1.4.2 Dose Rationale

For each subject, the starting dose of Y90-RE will be personalized based on the lobe and number of metastatic lesions. The actual dose will comply with the FDA-approved prescribing information (Appendix). Each subject will receive a fixed dose of 750mg of durvalumab with at least 2 weeks between doses depending on the dose level assigned to. This will coincide with the Tc99m labelled MAA eligibility mapping and treatment with Y90-RE and every 2 weeks visits with labs post Y90-RE, which is the preferred standard practice at most institutions. As noted in the study schema, there is margin for a few days before or after the planned 2-week cycle to accommodate scheduling issues. The timing and frequency of durvalumab varies on the dose level. Please discuss with the principal investigator and study clinical trial coordinator to know which dose level the patient is assigned to. From a safety perspective since we need to know about the shunting to other organs prior to the Y90-RE, the mapping can be done during the screening or even prior to considerations for this study if already performed within 12 months of intended Y90-RE, it would not need to be repeated unless as per interventional radiology.

Note: The dosing of Y90-RE, dose and administration will be as per FDA approved USPI. Goal is to deliver an ablative radiation dose to the targeted region and trigger a release of neo-antigens in order to augment immunotherapy; all the while minimizing collateral damage by sparing normal liver parenchyma. As noted in the protocol, there are numerous dosing methods in place for Durvalumab.

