4.0 Test Schedule

4.1 Test schedule for metastatic CRC

Tests and procedures	Screening		Active Monitoring Phase					
	Reg	Cycle 1	Cycle 2 (2 nd dose of Durva + Y90-RE)*	Cycle 3	Cycle 4	Cycle 5	End of treatment visit ¹²	Clinical Follow-up ¹³ (every 3 months)
Window	21 days	±5 days	±5 days	±5 days	±5 days	±5 days	±5 days	
History and exam ³ , Wt ⁵ , BP, HR, ECOG PS	X							
Exam, Wt ⁵ , BP, HR, ECOG PS		X	X	X	X	X	X	X
Adverse event assessment	X	X	X	X	X	X	X	X
Concomitant medication review	X	X	X	X	X	X	X	X
Height	X							
IR Consult	X							
Pregnancy test ¹	X		X		X		X	X
Hematology group CBC w/ 5-part differential	X	X	X	X	X	X	X	X
Chemistries ²¹	X	X	X	X	X	X	X	X
Thyroid Function Test TSH, free T4, amylase, lipase, Vitamin D	X		X		X		X	X
Creatinine clearance	X	X	X	X	X	X	X	X
Coagulation PT, PTT, INR	X						X	
Cholesterol, triglycerides	X							
IR Tc-99m labelled MAA eligibility mapping		X ¹⁸						
Tumor measurement ²	X						X	X
ECG ⁶	X		X		X		X	
Urinalysis ⁷	X	X	X	X	X	X	X	X
Administer durvalumab ^{8,R}		X ^{16,17,18,19}	X ^{9,16,17,18,19}	X ¹⁹	X ^{17,18,19}	X ^{17,18,19}		
Administer Y90-RE			X					
Patient Questionnaire Booklets ⁴ (Appendix III)		X	X	X	X	X	X	
Mandatory Research Specimens (see companion Lab Manual) ^{10,R}	X	X ^{14,15,16,17}	X ^{14,15,16,17}	X ¹⁷	X ^{15,16,17}	X ^{15,16,17}	X	
Mandatory Research Tissue specimens (see companion Lab Manual) 11,R	X (Pre- treatment) ₁₈						X (Post- treatment) _{19, 20}	

Cycle = 14 days

1. For women of childbearing potential only. Serum pregnancy test. Must be done \leq 7 days prior to registration.
2. A scan is required at baseline prior to the first dose of durvalumab. The scan does not need to be repeated as long as it is \leq 28 days prior to registration. Preferably we would recommend a CT of the chest and pelvis; and an MRI of the abdomen for assessment of liver metastases. If an MRI cannot be performed, a CT chest, abdomen, and pelvis would be acceptable. Please use same imaging throughout the study.
3. History and exam include prior surgery, cancer-related and other treatment and known positivity for Hepatitis B surface antigen, Hepatitis C virus antibodies, and Human Immunodeficiency Virus antibodies 1 /-2.
4. Patient questionnaire booklets **must** be used; copies are not acceptable for this submission
5. Body weight to be measured within 72 hours prior to durvalumab administration.
6. Single 12-lead ECG after 5 min rest in supine position.

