7.2 Return to consenting institution

For this protocol, the patient must return to the consenting institution for evaluation at least every 14 days during treatment and every 90 days during clinical follow-up (Active Monitoring Phase).

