7.4.2 Definitions of Dose Limiting Toxicities (DLT)

A DLT will be defined as any Grade 3 or higher treatment-related toxicity that occurs during the DLT observation phase (8 weeks post Y90-RE), including:

- Any event resulting in a delay of cycle 2 by \geq 14 calendar days
- Any Grade 4 immune related adverse event (irAE)
- Any Grade 3 immune related AE (irAE) that does not resolve to \leq Grade 1 or to baseline with immunosuppressive therapy within 3 weeks
- Any Grade 3 colitis
- Any Grade 3 noninfectious pneumonitis irrespective of duration
- Grade 4 neutrophil count decreased lasting longer than 5 calendar days
- Grade 4 platelet count decreased
- Grade 3 platelet count decreased with hemorrhage
- Any \geq Grade 2 pneumonitis that does not resolve to \leq Grade 1 within 7 days of the initiation of maximal supportive care
- Any other Grade 3 irAE (excluding colitis or pneumonitis), that does not downgrade to Grade 2 within 7 days after onset of the event despite optimal medical management including systemic corticosteroids or does not downgrade to \leq Grade 1 or baseline within 14 days
- Liver transaminase elevation $> 8 \times$ ULN
- Total bilirubin $> 5 \times$ ULN
- AST or ALT $> 5-8 \times$ ULN with concurrent increase in total bilirubin $> 2 \times$ ULN without evidence of cholestasis or alternative explanations, e.g., viral hepatitis, disease progression in the liver, etc. (Hyll's Law). Exception: If it is present at cycle 3 but resolves at cycle 4 it is not a DLT.
- Any \geq grade 3 non-hematologic toxicity, except:
 - Grade 3 nausea or vomiting that lasts < 48 hours and resolves to \leq Grade 1 either spontaneously or with conventional medical intervention
 - Grade 3 nausea, vomiting, and diarrhea lasting < 72 hours in the absence of maximal medical therapy
 - Grade 4 vomiting and diarrhea lasting < 72 hours in the absence of maximal medical therapy
 - Grade 3 hypertension in the absence of maximal medical therapy
 - Grade 3 metabolic abnormalities (e.g. hypokalemia, hypomagnesemia, hypocalcemia, hypophosphatemia) that recover to \leq Grade 1 within 48 hours
 - \geq Grade 3 electrolyte abnormality lasting < 72 hours, is not clinically complicated, and resolves spontaneously or responds to conventional medical intervention.
 - Grade 3 or 4 elevation in serum amylase and/or lipase that are not associated with clinical or radiographic evidence of pancreatitis.
 - Grade 3 rash < 5 calendar days

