 - Grade 3 rash that resolves to \leq Grade 1 within 3 weeks
 - Grade 3 fatigue lasting ≤ 7 days
 - Grade 3 endocrine disorder (thyroid, pituitary, and/or adrenal insufficiency) that is managed with or without systemic corticosteroid therapy and/or hormone replacement therapy and the subject is asymptomatic

- Grade 3 inflammatory reaction attributed to a local antitumor response (e.g., inflammatory reaction at sites of metastatic disease, lymph nodes)
- Concurrent vitiligo or alopecia of any AE grade
- Grade 3 infusion-related reaction (first occurrence and in the absence of steroid prophylaxis) that resolves within 6 hours with appropriate clinical management
- Grade 3 or 4 neutropenia that is not associated with fever or systemic infection that improves by at least 1 grade within 7 days. Grade 3 or Grade 4 febrile neutropenia will be a DLT regardless of duration or reversibility

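### Neutropenia counts as a DLT by how long it lasts, but fortnightly blood counts cannot show that duration and the two neutropenia rules in Section 7.4.2 imply opposite defaults when it is unknown

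*Combined protocol and SAP*

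**What the plan says.** **Duration rules (Section 7.4.2).** The list of DLTs includes "Grade 4 neutrophil count decreased lasting longer than 5 calendar days". Further down, among the exceptions, afebrile Grade 3 or 4 neutropenia without systemic infection is released if it "improves by at least 1 grade within 7 days". Febrile neutropenia of Grade 3 or 4 is a DLT whatever its duration. Two other laboratory exceptions also carry time limits: Grade 3 metabolic abnormalities that recover within 48 hours, and, at that grade or above, "Grade 3 electrolyte abnormality lasting < 72 hours".

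**Blood schedule.** The test schedule in Section 4.1 lists "Hematology group CBC w/ 5-part differential" and chemistries once per 14-day cycle with a ±5-day window, and again at the end-of-treatment visit 8 weeks after Y90-RE. Section 1.4.2 describes "every 2 weeks visits with labs post Y90-RE". Section 7.2 says "the patient must return to the consenting institution for evaluation at least every 14 days during treatment", and Section 17.2 gives the same interval with ±5 days. Scheduled blood after Y90-RE in the DLT window is therefore at about weeks 2, 4, 6 and 8.

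**Repeat testing.** Closer follow-up of an abnormal result is described for liver tests (Section 9.5.6, Appendix VII) and creatinine (Appendix VII). There is no such rule for neutrophils or electrolytes, and Table 8.21 has no hematologic row. Nothing in Section 7.4.2 says how to classify an event whose duration is not known.

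**Escalation.** Under Sections 1.4.6 and 17.2, one patient is treated per level until a first DLT is recorded.

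**The concern.** DLT status here depends on limits of 5 and 7 days, while the planned observations are 14 days apart. A Grade 4 neutrophil count found at one visit and gone at the next has an unknown duration, so its classification depends on whether someone ordered an extra test, or on which of the two rules the assessor applies. Safety is the primary goal, and in the accelerated phase a single patient without a recorded DLT is enough to move up a level. Two assessors could read the same record differently and reach opposite escalation decisions.

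**Working it through.** **1. The plan's own figure.** The plan gives no probability of detecting a time-limited laboratory toxicity. The nearest figure is in Section 17.2: a toxicity with 25% incidence is seen at least once in 6 patients with probability 1 − (1 − 0.25)^6 = 0.822, which reproduces the stated 82%. It takes every occurrence as observed. It concerns common toxicities at the MTD and is not in dispute here.

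**2. What two draws can show.** Suppose a Grade 4 count appears at one scheduled draw and at neither neighbor.
- At exact spacing the neighboring draws are 2 × 14 = 28 days apart, so the episode lasted somewhere between a moment and just under 28 days. Both the 5-day and the 7-day limit lie inside that range.
- To prove more than 5 days from scheduled blood alone, two draws more than 5 days apart must both fall in the episode. For a 6-, 7- or 8-day episode this is impossible at exact 14-day spacing.
- In a simulation with each draw shifted uniformly by up to 5 days (an assumption; 1,000,000 runs), it happened in about 0.0% of 6-day and 0.2% of 7-day episodes.

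**3. The two neutropenia rules side by side, for afebrile Grade 4 neutropenia.**
- Grade 4 for 5 days or less, then improving: not met as a listed DLT, and excepted. The rules agree on no DLT.
- Grade 4 for 6 days, then improving: a listed DLT, yet excepted because it improved within 7 days. The rules conflict even when duration is known.
- Grade 4 for 8 days: a listed DLT, and not excepted. The rules agree on a DLT.
- Duration unknown: the listed criterion is not shown to be met, which points to no DLT. The exception is not shown to be met either, which points to a DLT.

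The exception also stands in the list of exceptions to non-hematologic toxicity, where a neutropenia rule does not belong, so its reach is itself unclear.

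**4. Chance that scheduled blood sees the episode.** Assume random onset, draws exactly 14 days apart and no unscheduled tests. For an episode of d days with d < 14, P(seen) = d/14.
- 8 days (a DLT under both rules): 8/14 = 57%, so 43% are unseen.
- 6 days (the rules conflict): 6/14 = 43%, so 57% are unseen.

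The visit window hardly changes the average: with the same uniform shifts the 6-day figure was 42.7%. The extreme gap is 14 + 5 + 5 = 24 days, giving 8/24 = 33% and 6/24 = 25%, but this needs both visits at opposite ends of their windows.

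**5. The 48-hour and 72-hour exceptions.** These are carved out of a general rule that any non-hematologic toxicity of Grade 3 or higher is a DLT. A detected value without documented timely recovery does not earn the exception and remains a DLT. The default is therefore settled by the structure of the section. What is lacking is a scheduled draw that could verify the exception.

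**The case against.** **The interval is only a minimum, and clinicians will repeat a Grade 4 count.** This is true and reduces the effect. But the repeat is not required, so DLT classification is left to individual practice, and an episode that nobody saw prompts no repeat. The table for non-immune-mediated reactions (Appendix VIII) has 7-day and 14-day limits for Grade 3 events, which implies reassessment between visits. It governs resumption of study drug, however, and schedules no draw.

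**Neutropenia may be rare here.** It is not among the durvalumab toxicities in Section 15.17 or in the TheraSphere adverse-event tables in Appendix VI. Entry requires a neutrophil count of at least 1500/mm³ and 14 days without chemotherapy. Febrile cases count regardless of duration, and the Grade 4 platelet, transaminase and bilirubin criteria have no time limit. This stands, and it limits the size of the point.

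**The opening sentence of Section 7.4.2 counts any treatment-related toxicity of Grade 3 or higher, so unknown duration means a DLT.** Read that way, the 5-day condition on Grade 4 neutrophils would have no function. A reader who gives the condition effect reaches the opposite answer, so the ambiguity remains.

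**A reader might infer a wider defect:** that all the time-limited laboratory criteria are compromised and that the schedule biases the trial toward calling levels tolerable. The documents do not support this. A detected electrolyte or metabolic value of undocumented duration stays a DLT, which is conservative. The low chance of seeing a 2- or 3-day electrolyte episode mostly concerns events that would be excepted anyway.

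**Conclusion.** The point holds for neutropenia. Its duration cannot be established from scheduled draws, the listed criterion and the exception disagree on some episodes of known duration, and they imply opposite answers when duration is unknown. In the single-patient phase that answer decides whether the level is cleared.

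Scheduled blood sees 57% of 8-day and 43% of 6-day Grade 4 episodes, given random onset, exact 14-day spacing and no unscheduled tests. These are detection figures for one kind of event and do not measure how many DLTs the trial would miss. The effect on escalation cannot be sized because the documents give no neutropenia rate, and it is smaller than these percentages suggest for the reasons above. For the 48-hour and 72-hour exceptions, the finding is only that they cannot be verified from scheduled draws. This should be corrected because DLTs drive every escalation decision and the correction is cheap, but it does not undermine the design as a whole.

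**What to change.** 1. Reconcile the two neutropenia rules in Section 7.4.2, including where the exception is placed, so that each episode has one classification. Which limit applies is for the investigators to decide.
2. Add a counting rule to Section 7.4.2: for any time-limited laboratory criterion or exception, duration runs from the first abnormal value to the first recovered value. If recovery within the limit is not documented, the event counts as exceeding the limit.
3. State in Sections 4.1 and 7.2 that within the DLT window a Grade 3 or higher neutrophil or electrolyte value is repeated before the applicable limit ends.

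The cost is protocol wording, a few repeat routine blood tests in a trial of 18 patients, and a slightly more conservative DLT count. A routine weekly draw for everyone is optional and not part of this fix. It would raise the chance of seeing a 6-day episode to 6/7 = 86%, but would not by itself verify a 48-hour, 72-hour or 5-day limit.

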Grade 2 AST, ALT, or TBIL AST or ALT $> 3.0 - 5 \times \text{ULN}$ and/or TBIL $> 1.5 - 3 \times \text{ULN}$	
 Hold study drug/study regimen dose until resolution to AST or ALT $\leq 3.0 \times \text{ULN}$ and/or TB $\leq 1.5 \times \text{ULN}$. If toxicity worsens, then treat as described for elevations in the row below. If toxicity improves to AST or ALT $\leq 3.0 \times \text{ULN}$ and/or TB $\leq 1.5 \times \text{ULN}$, or baseline, resume study drug/study regimen after completion of steroid taper. 	
 Regular and frequent checking of LFTs (e.g., every 1 to 2 days) until elevations of these are improving or resolved. If no resolution to AST or ALT $\leq 3.0 \times \text{ULN}$ and/or TB $\leq 1.5 \times \text{ULN}$ in 1 to 2 days, consider, as necessary, discussing with study physician. If event is persistent (> 3 to 5 days) or worsens, promptly start prednisone 1 to 2 mg/kg/day PO or IV equivalent. If still no improvement within 3 to 5 days despite 1 to 2 mg/kg/day of prednisone PO or IV equivalent, consider additional work up and start prompt treatment with IV methylprednisolone 2 to 4 mg/kg/day. If still no improvement within 3 to 5 days despite 2 to 4 mg/kg/day of IV methylprednisolone, promptly start immunosuppressives (i.e., mycophenolate mofetil).^a Disyycess with study physician if mycophenolate mofetil is not available. Infliximab should NOT be used. Once the patient is improving, gradually taper steroids over ≥ 28 days and consider prophylactic antibiotics, antifungals, and anti-PJP treatment (refer to current NCCN guidelines for treatment of cancer-related infections [Category 2B recommendation]).^a
AST or ALT $> 5.0 \times \text{ULN}$ and/or	For elevations in transaminases $\leq 8 \times \text{ULN}$ or elevations in TBIL $\leq 5 \times \text{ULN}$:	
 Promptly initiate empiric IV methylprednisolone at 1 to 4 mg/kg/day or equivalent. If still no improvement within 3 to 5 days despite 1 to 4 mg/kg/day methylprednisolone IV or equivalent, promptly start treatment with

Severity (CTCAE v 5.0)	Dose Modifications	Toxicity Management

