TBIL $>3.0 \times$ ULN	
 Hold study drug/study regimen dose until resolution to AST or ALT $\leq 3.0 \times$ ULN and/or TB $\leq 1.5 \times$ ULN, or baseline Resume study drug/study regimen if elevations downgrade to AST or ALT $\leq 3.0 \times$ ULN and/or TB $\leq 1.5 \times$ ULN, or baseline within 14 days and after completion of steroid taper. Permanently discontinue study drug/study regimen if the elevations do not downgrade to AST or ALT $\leq 3.0 \times$ ULN and/or TB $\leq 1.5 \times$ ULN or baseline within 14 days. 
For elevations in transaminases $>8 \times$ ULN or elevations in bilirubin $>5 \times$ ULN, permanently discontinue study drug/study regimen.
 
Permanently discontinue study drug/study regimen for any case meeting Hy's law criteria (AST and/or ALT $>3 \times$ ULN + bilirubin $>2 \times$ ULN without initial findings of cholestasis (i.e., elevated alkaline phosphatase) and in the absence of any alternative cause.^b Note that this does not apply to the week 2 (cycle 3) post Y90-RE when this is usually seen and subsides in the upcoming weeks (cycle 4). Also for those with Gilbert's syndrome, would need to rely on AST/ALT rather than total bilirubin.
	
 immunosuppressive therapy (i.e., mycophenolate mofetil). Discuss with study physician if mycophenolate is not available. Infliximab should NOT be used. Perform hepatology consult, abdominal workup, and imaging as appropriate. Once the patient is improving, gradually taper steroids over ≥ 28 days and consider prophylactic antibiotics, antifungals, and anti-PJP treatment (refer to current NCCN guidelines for treatment of cancer-related infections [Category 2B recommendation]).^a

Nephritis or renal dysfunction (elevated serum creatinine)

Any Grade	General Guidance	
		
 Consult with nephrologist. Monitor for signs and symptoms that may be related to changes in renal function (e.g., routine urinalysis, elevated serum BUN and creatinine, decreased creatinine clearance, electrolyte imbalance, decrease in urine output, or proteinuria). Patients should be thoroughly evaluated to rule out any alternative etiology (e.g., disease progression or infections). Steroids should be considered in the absence of clear alternative etiology even for low-grade events (Grade 2), in order to prevent potential progression to higher grade event.

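### The Hy's law DLT in Section 7.4.2 starts at AST/ALT >5 × ULN while Appendix VII starts at >3 × ULN, so a narrow band of cases is Hy's law by the appendix but no DLT

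*Combined protocol and SAP*

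**What the plan says.** Section 7.4.2 opens by defining a DLT as a treatment-related toxicity of Grade 3 or higher in the 8 weeks after Y90-RE, and then lists events. Three of them concern the liver: transaminases >8 × ULN; total bilirubin >5 × ULN; and AST or ALT >5–8 × ULN together with bilirubin >2 × ULN, "without evidence of cholestasis or alternative explanations, e.g., viral hepatitis, disease progression in the liver, etc. (Hyll's Law"). The misspelled name is plainly Hy's law. A case seen at cycle 3 that has gone by cycle 4 is excused. A general line covers any "grade 3 non-hematologic toxicity, except" for a list of exceptions that contains no liver test. One listed event lies below Grade 3: "Grade 2 pneumonitis that does not resolve to" Grade 1 or less within 7 days.

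The hepatitis table of Appendix VII says: "Permanently discontinue study drug/study regimen for any case meeting Hy's law criteria (AST and/or ALT" >3 × ULN with bilirubin >2 × ULN), "without initial findings of cholestasis (i.e., elevated alkaline phosphatase) and in the absence of any alternative cause". It adds: "Note that this does not apply to the week 2 (cycle 3) post Y90-RE". That sentence is printed in the row for AST/ALT >5 × and/or bilirubin >3 × ULN. The Grade 2 row above it (AST/ALT >3–5 ×, bilirubin >1.5–3 × ULN) says to hold treatment and, on improvement below the Grade 2 limits "or baseline, resume study drug/study regimen after completion of steroid taper". Table 8.21 in Section 8.2 also says hold at Grade 2, with a permanent stop if the event has not settled within 2 weeks. Section 8.0 makes the modifications in that table strict for the first two cycles only and guidance afterwards.

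**The concern.** One named safety signal has two transaminase limits, with exclusions for cholestasis and other causes that match in substance. The higher limit sits in the rule that decides escalation. Liver injury is the main overlapping risk of liver radioembolization and a PD-L1 inhibitor. Under Section 1.4.6, one DLT-free patient clears a dose level until the first DLT is recorded. The question is whether a case that the protocol's own appendix would call Hy's law can pass through that rule uncounted.

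**Working it through.** The plan gives no figure on this point, so there is none to reproduce. The check sets the texts side by side.

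**1. Bands.** The grades are those of the Appendix VII rows.

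| AST/ALT (× ULN) | Bilirubin (× ULN) | Hy's law limits, Appendix VII | DLT, Section 7.4.2 |
|---|---|---|---|
| >3–5 | >2–3 | met | no (both Grade 2) |
| >3–5 | >3 | met | yes (bilirubin above Grade 2) |
| >5 | >2 | met | yes (AST/ALT above Grade 2) |

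**2. The first row against every line of 7.4.2.** The header and the general non-hematologic line need Grade 3. The other liver lines need >8 × or >5 × ULN. The irAE lines need Grade 3 or 4. The delay line concerns cycle 2, the cycle in which Y90-RE is given, so an event after Y90-RE cannot trigger it. The pneumonitis, colitis and blood-count lines do not apply. No line is met.

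**3. Grid check.** AST/ALT 1.0–12.0 and bilirubin 0.5–8.0 × ULN, in steps of 0.1. Points that meet the appendix limits but are no DLT:
- All lines applied: AST/ALT 3.1–5.0 by bilirubin 2.1–3.0, that is 20 × 10 = 200 points.
- Liver-specific lines alone: bilirubin 2.1–5.0, that is 20 × 30 = 600 points. The Grade 3 line therefore closes most of the gap.
- Limit in the 7.4.2 line lowered to >3 × ULN: 0 points, leaving the cycle 3 exception aside.

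**4. What the 7.4.2 line adds.** AST/ALT >5 × ULN is already above the Grade 2 band, so the line creates no DLT that the Grade 3 lines miss. Its only separate content is the exception, which clashes with those lines. Take AST 6 × and bilirubin 2.5 × ULN at cycle 3, resolved at cycle 4. The exception says no DLT, but the general line still scores the AST.

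**5. Effect on a decision.** In the single-patient phase, an uncounted case means escalation instead of two more patients and a switch to 3+3. In 3+3, one in-band case plus one scored DLT among three reads as 1/3 (expand) instead of 2/3 (stop). At dose level 1 (Section 7.4.1) both durvalumab doses come before Y90-RE. A stop under Appendix VII then has nothing left to withhold, and the DLT count is the only stated escalation rule through which the case could act.

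**6. Size, by assumption only.** Let q be the per-patient rate of in-band cases, s the rate of DLTs scored now, and r = 1 − s − q. With one patient per level, the chance of at least one uncounted case at levels 1–3 before the first scored DLT is q(1 + r + r²).

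| | q = 1% | q = 2% | q = 5% |
|---|---|---|---|
| s = 0 | 0.030 | 0.059 | 0.143 |
| s = 10% | 0.027 | 0.053 | 0.129 |
| s = 20% | 0.024 | 0.048 | 0.116 |

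For example, s = 20% and q = 5% give 0.05 × (1 + 0.75 + 0.5625) = 0.116. The documents supply neither q nor s.

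**7. Price of counting these cases.** A level with DLT rate p passes 3+3 with probability (1 − p)³ + 3p(1 − p)⁵. At p = 10% this is 0.729 + 0.177 = 0.906. Adding 1, 2 or 5 points gives 0.889, 0.871 or 0.814. At p = 20% it is 0.709, falling to 0.687, 0.665 or 0.600.

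**The case against.** The strongest reply is that the two texts do different jobs. Section 7.4.2 steers escalation, Appendix VII steers one patient's drug, and a higher limit for escalation can be defended. Section 1.4.5 expects raised liver enzymes in most patients for 1–2 weeks after Y90-RE. The package insert (Appendix VI) reports raised AST in 86.2%, ALT in 56.2% and bilirubin in 41.2% of its HCC review, all grades. Section 3.2.1 admits patients with AST/ALT up to 2.5 × and bilirubin up to 1.5 × ULN (or 2.0 mg/dL if lower), so a small rise could cross a bare >3 ×/>2 × limit. Deleting the Hy's law label would also end the mismatch.

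Part of this stands. A bare limit would be too sensitive, so the rule needs a baseline condition and a confirming test. But 7.4.2 itself names Hy's law as a DLT, already handles the early rise through the cycle 3/cycle 4 exception, already lists a Grade 2 event, and gives no reason for a different number. Deleting the label would leave a line that adds no DLT and an exception that is still contradicted.

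The small size of the group also stands. Appendix VII counts raised alkaline phosphatase as cholestasis, and the package insert says most patients have a transient rise (29.7% in its HCC review). Liver metastases often offer another cause. A case that passes 5 × or 3 × ULN within the 8 weeks is scored anyway, and Section 17.2 makes new patients wait that long.

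A reader might infer that every in-band patient must stop permanently and yet goes uncounted. The documents do not support that: the Hy's law sentence sits in the >5 × row, the Grade 2 row and Table 8.21 say hold, and Section 8.0 relaxes its table to guidance after cycle 2. Nor must every stop be a DLT. Table 8.21 stops treatment for a Grade 3 infusion reaction, while 7.4.2 excuses a first one that resolves within 6 hours.

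**Conclusion.** The mismatch is real and narrow. A treatment-related, non-cholestatic, otherwise unexplained case after Y90-RE, outside the cycle 3 exception, that stays at AST/ALT >3–5 × and bilirubin >2–3 × ULN through the window meets the appendix limits for Hy's law and no DLT line. In the single-patient phase it would not prevent escalation. The 7.4.2 line is redundant with the Grade 3 lines, and its exception contradicts them.

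This is a minor safety-rule correction. It rests on the Appendix VII grade bands and on reading the general Grade 3 line as covering liver tests. A reader might take the 2–14% range as an estimate of risk. It is illustration only: every rate is assumed, the filters above argue against q as high as 5%, and the top value needs s = 0. Section 17.3 does expect no DLTs, but Section 1.2.2 cites Grade 3 or 4 hyperbilirubinemia in 13% of 531 glass-microsphere patients (not all necessarily treatment-related or within 8 weeks).

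**What to change.** - **7.4.2 liver line.** Restate as AST or ALT >3 × ULN with concurrent total bilirubin >2 × ULN, confirmed on a repeat test and representing a rise from baseline, without cholestasis (raised alkaline phosphatase) or another explanation. Carry over the Appendix VII wording for Gilbert's syndrome. The repeat is little extra work, since the Grade 2 row already asks for "Regular and frequent checking of LFTs (e.g., every 1 to 2 days) until elevations of these are improving or resolved".
- **Exception.** Keep the cycle 3/cycle 4 exception and list it under the Grade 3 non-hematologic line too. Confine it to values that do not exceed the separate >8 × and >5 × ULN lines, because the restated limit no longer has an upper end.
- **Header of 7.4.2.** Extend it to any event listed beneath it, whatever the grade. This also regularizes the Grade 2 pneumonitis line.
- **Appendix VII, Grade 2 row.** State that confirmed Hy's law cases follow the permanent stop, and cross-refer from Table 8.21.

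Cost: wording only, with no new scheduled tests, since Section 4.1 already has chemistries at every cycle and at end of treatment. The Summary of Changes records FDA-requested edits to 7.4.2, so FDA and IRB review is probable. A few more DLTs may be declared, some from Grade 2 laboratory values, which lowers the chance that a level passes by the amounts in step 7 of the working. The repeat and baseline conditions should limit this.
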